Study Design: In this safety study of nivolumab monotherapy, subjects will undergo screening evaluations to determine eligibility within 28 days prior to first dose. Eligible subjects will be treated with nivolumab administered intravenously over 30 minutes at 3 mg/kg every two weeks. Each 14 day dosing period will constitute a cycle. After 1 year (52 weeks) of treatment all subjects who are still on treatment will be randomized (1:1) to one of the two cohorts, Cohort A or Cohort B.

- Cohort A: Subjects randomized to Cohort A will continue to receive treatment until disease progression, unacceptable toxicity, or withdrawal of informed consent.
- Cohort B: Subjects randomized to Cohort B will discontinue treatment at 1 year (52 weeks). After randomization, subjects will remain on the study and will follow all study assessments [REDACTED] Upon progression, subjects can receive retreatment. If subjects are [REDACTED]

[REDACTED] Subjects who are retreated can continue to receive study drug until further progression, unacceptable toxicity, or withdrawal of informed consent.

Study treatment can continue beyond initial investigator assessed progression, as specified in criteria presented in [Section 4.3.4 Treatment Beyond Disease Progression](#).

The study will enroll subjects into 4 subgroups as detailed in [Table 3.1-1](#). Enrollment will open first to subgroup 1 only. A decision to open enrollment for each of the other subgroups 2-4 will be dependent upon the sponsor review of data from the ongoing Phase 2 and 3 studies for each patient population. The decision will take into account the overall risk/benefit profile for each patient population and the determination will be made whether or not to collect additional safety and efficacy data to supplement that already collected.

At the time of Protocol Amendment 01 (June 2014), all subgroups were opened.

Protocol Amendment 03 (November 2014) allowed for continued enrollment beyond 780 subjects in two of the study subgroups. However, as of Protocol Amendment 04 (December 2014), enrollment under Amendment 03 will stop, but enrollment will continue until 500 additional subjects are treated. Enrollment will continue until a total of 1280 subjects are treated.

[REDACTED]

Under Protocol Amendment 04, all subjects will receive nivolumab by IV infusion administered over 30 minutes, including new and existing subjects enrolled in the study and subjects enrolled under Amendment 02.

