The study will close after the last enrolled subject completes 5 year follow up. The duration of the study will be 6.5 years.

Study Population: Patients with Stage 3b/4 NSCLC (squamous or non-squamous histology) who have experienced disease progression or recurrence during or after at least one systemic therapy for advanced or metastatic disease. Subjects must meet all eligibility criteria specified in [Section 3.3](#) of the protocol.

Study Assessments: Main assessments include: Incidence, severity and outcome of select adverse events, and specific related laboratory abnormalities. Exploratory assessments include incidence and severity of all adverse events, laboratory abnormalities, efficacy measures, patient reported outcomes [REDACTED].

Statistical Considerations:

Sample Size: In order to further characterize the frequency and outcome of the rather infrequent treatment related select adverse of high grade (Grade 3-5), the current study will treat approximately 780 subjects with nivolumab. This sample size will allow for estimating an incidence rate of 0.5% (n=4 subjects with events) with a 95% CI (confidence interval) of (0.14%, 1.31%), or an incidence rate of 2% (n=16 subjects with events) with a 95% CI of (1.18%, 3.31%).

This study also includes a randomization step reserved to subjects who received nivolumab for 1 year (52 weeks). In MDX1106-03, 27% of NSCLC subjects (10 of 37) were still on treatment [95% CI of (12.7%, 41.3%)] at Week 48. In the present study any subjects (all subgroups included) who are still benefiting from therapy after 52 weeks (estimated to be between 99 and 322 subjects) will be randomized in order to continue treatment without any change in Cohort A, or to discontinue treatment in Cohort B, respectively.

Endpoints: The primary objective of the study will be assessed by measuring the incidence for high grade (Grade 3-4 and Grade 5) treatment related select adverse events.

The select adverse events of interest are the following: pneumonitis, interstitial nephritis, diarrhea/colitis, hepatitis, rash, endocrinopathies, and hypersensitivity/infusion reaction events.

The secondary objective of the study will be assessed by measuring the following:

- incidence for high grade (Grade 3-4 and Grade 5) select adverse events
- median time to onset, median time to resolution (Grade 3-4) of the select adverse events

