3 INVESTIGATIONAL PLAN

3.1 Study Design and Duration

In this safety study of nivolumab monotherapy, subjects will undergo screening evaluations to determine eligibility within 28 days prior to first dose. Eligible subjects will be treated with nivolumab administered intravenously over 30 minutes at 3 mg/kg every two weeks. Each

14 day dosing period will constitute a cycle. After 1 year (52 weeks) of treatment all subjects who are still on treatment will be randomized (1:1) to one of the two cohorts, Cohort A or Cohort B.

- Cohort A: Subjects randomized to Cohort A will continue to receive treatment until disease progression, unacceptable toxicity, or withdrawal of informed consent.
- Cohort B: Subjects randomized to Cohort B will discontinue treatment at 1 year (52 weeks). After randomization, subjects will remain on the study and will follow all study assessments [REDACTED]. Upon progression, subjects can receive retreatment.

Subjects who are retreated can continue to receive study drug until further progression, unacceptable toxicity, or withdrawal of informed consent.

Study treatment can continue beyond initial investigator assessed progression, as specified in criteria presented in [Section 4.3.4 Treatment Beyond Disease Progression](#). The study will close after the last enrolled subject completes 5 year follow up.

The study will enroll subjects into 4 subgroups as detailed in [Table 3.1-1](#).

Enrollment will open first to subgroup 1 only. A decision to open enrollment for each of the other subgroups 2-4 will be dependent upon the sponsor review of data from the ongoing Phase 2 and 3 studies for each patient population. The decision will take into account the overall risk/benefit profile for each patient population and the determination will be made whether or not to collect additional safety and efficacy data to supplement that already collected.

At the time of Protocol Amendment 01 (June 2014), all subgroups were opened.

Protocol Amendment 03 (November 2014) allowed for continued enrollment beyond 780 subjects in two of the study subgroups. However, as of Protocol Amendment 04 (December 2014), enrollment under Amendment 03 will stop, but enrollment will continue until 500 additional subjects are treated. Enrollment will continue until a total of 1280 subjects are treated.

[REDACTED]

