4.1 Study Treatments

Nivolumab 100 mg (10 mg/mL) will be packaged in an open-label fashion. Ten BMS-936558 (nivolumab), 10 mL vials will be packaged within a carton (see [Table 4.1-1](#)), and are not subject or treatment arm specific. Vial assignments by subject will be made through the IVRS (interactive voice response system) to track usage and resupply.

As described in [Section 3.1](#), nivolumab will be dosed intravenously at 3 mg/kg every two weeks. After 1 year (52 weeks) of treatment the subjects who are still on the study and benefiting from the therapy will be randomized (1:1) via IVRS to one of the two cohorts, Cohort A or Cohort B.

Subjects randomized to Cohort A will be treated until disease progression, unacceptable toxicity, or withdrawal of informed consent. Subjects randomized to Cohort B will discontinue treatment at 1 year (52 weeks). Subjects in Cohort B will remain on the study and will follow all study assessments [REDACTED]. At progression, subjects in Cohort B may receive retreatment [REDACTED].

Subjects who are retreated can continue until progression, unacceptable toxicity, or withdrawal of informed consent. Study treatment can continue beyond initial investigator assessed progression, as specified in criteria presented in [Section 4.3.4 Treatment Beyond Disease Progression](#).

Table 4.1-1: Product Description

Product Description and Dosage Form	Potency	Primary Packaging (Volume)/ Label Type	Secondary Packaging (Qty) /Label Type	Appearance	Storage Conditions (per label)
BMS-936558-01 Solution for Injection	100 mg (10 mg/mL)	10 mL vial/ Open-label	10 vials per carton/ Open-label	Clear to opalescent, colorless to pale yellow liquid. May contain particles.	2 to 8° C. Protect from light, shaking, and freezing.

NOTE: Medications used to treat BMS-936558 (nivolumab)-related infusion reactions are (eg, diphenhydramine, acetaminophen/paracetamol, corticosteroids) considered NIMPs (noninvestigational products) and will not be provided by the sponsor. These will be obtained by the investigational sites as marketed product, which should be stored in accordance to the package insert. For further details related to these medications and BMS-936558 (nivolumab)-related infusion reactions, please see [Section 4.3.6](#).

4.1.1 *Investigational Product*

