4.2 Method of Assigning Subject Identification

After the subject's eligibility is established and informed consent has been obtained, the subject will be enrolled and a number will be assigned through an interactive voice response system (IVRS). Also, the IVRS will be used to manage staggered enrollment of subject subgroups, and to randomize subjects at 1 year (52 weeks, \pm 2 weeks) as well as to track the randomized subjects from subgroups to cohorts. Specific instructions and procedures for using IVRS will be provided to the investigational site in a separate document/ manual.

The investigator (or designee) will register the subject for enrollment by following the enrollment procedures established by BMS. The following information is required for enrollment:

- Date of informed consent
- Date of birth
- Gender at birth
- Diagnosis (ie, SQ or NSQ NSCLC)
- Number of lines of therapy with confirmed progression
- PS

The subjects who complete 1 year (52 weeks) of study treatment and are still benefiting from the nivolumab treatment will be randomized (1:1) via IVRS to one of the two cohorts, Cohort A or Cohort B.

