4.3.4 Treatment Beyond Disease Progression

As described in [Section 1.4.3.3](#), accumulating evidence indicates a minority of subjects treated with immunotherapy may derive clinical benefit despite initial evidence of PD. Subjects treated with nivolumab will be permitted to continue treatment beyond initial RECIST 1.1 defined progressive disease (PD) as long as the following criteria are met:

- 1) Investigator-assessed clinical benefit and do not have rapid disease progression
- 2) Tolerance of study drug
- 3) Stable performance status
- 4) Treatment beyond progression will not delay an imminent intervention to prevent serious complications of disease progression (eg, CNS metastases)
- 5) Subject provides written informed consent prior to receiving additional nivolumab treatment, using an ICF describing any reasonably foreseeable risks or discomforts, or other alternative treatment options.

The decision to continue treatment beyond initial progression should be discussed with the BMS medical Monitor and documented in the study records.

A radiographic assessment/ scan should be performed within 8 weeks of original PD to determine whether there has been a decrease in the tumor size, or continued PD. The assessment of clinical benefit should be balanced by clinical judgment as to whether the subject is clinically deteriorating and unlikely to receive any benefit from continued treatment with nivolumab.

If the investigator feels that the nivolumab subject continues to achieve clinical benefit by continuing treatment, the subject should remain on the trial and continue to receive monitoring according to the Time and Events Schedule on [Table 5.1-2](#).

For the subjects who continue nivolumab study therapy beyond progression, further progression is defined as an additional 10% increase in tumor burden volume from time of initial PD. This includes an increase in the sum of all target lesions and/ or the development of new measurable lesions. Treatment should be discontinued permanently upon documentation of further disease progression

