Radiographic tumor assessments				X	
At Week #9 (the 9th week on study with C1D1 week counted as week #1) \pm 5 days and every 8 weeks (\pm 5 days) thereafter up to 24 months from first dose then every 12 weeks (\pm 5 days) regardless of dosing schedule, until documented disease progression or discontinuation of study therapy in subjects receiving nivolumab beyond progression.
 
Assessments should include all areas that are being monitored and new areas if clinically indicated (with contrast unless contraindicated). Follow RECIST 1.1 criteria.
 
Subjects with a history of brain metastasis (BM) should have surveillance MRI approximately every 12 weeks, or sooner if clinically indicated.
 
After 24 months of treatment, the frequency of surveillance brain MRI or CT scans will be every 6 months or earlier, if clinically indicated, for subjects with known brain metastases.

Table 5.1-2: On-Study Procedural Outline (CA209153)

Procedure	C1D1 (Cycle 1 Day 1)	Each Cycle (Every 2 weeks) on Day 1	Every 3 Cycles (Every 6 weeks) on Day 1	Every 4 Cycles (Every 8 weeks) on Day 1	Notes
Randomization		At 1 year (52 weeks)			Subjects that are still on study and benefiting from treatment will be randomized 1:1 to Cohort A or B.

Table 5.1-2: On-Study Procedural Outline (CA209153)

Procedure	C1D1 (Cycle 1 Day 1)	Each Cycle (Every 2 weeks) on Day 1	Every 3 Cycles (Every 6 weeks) on Day 1	Every 4 Cycles (Every 8 weeks) on Day 1	Notes
Administration of nivolumab (BMS-936558) 3 mg/kg	X	X			
All subjects start treatment on C1D1 and continue treatment every 2 weeks until disease progression, unacceptable toxicity, or withdrawal of informed consent. At 1 year (52 weeks) all subjects that remain on treatment will be randomized to Arm A or Arm B.
 
Cohort A subjects will continue treated until disease progression, unacceptable toxicity, or withdrawal of informed consent.
 
Cohort B subjects will discontinue treatment at 1 year (52 weeks \pm 2 weeks). Upon progression, subjects can be retreated until progression, unacceptable toxicity, or withdrawal of informed consent.
 
Treatment for all subjects can continue beyond initial investigator-assessed progression as specified in Section 4.3.4. Drug administration is $+/-$ 3 days but no less than 12 days from previous dose. Study drug infusion start and stop times will be recorded. .

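### As visibly written, subjects treated past first RECIST progression can be randomised at week 52, so some Cohort A/B PFS and DOR events predate allocation

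*Combined protocol and SAP*

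**What the plan says.** Who is randomised is worded in two ways.

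- **Still on treatment.** The synopsis design text and Section 3.1 ("all subjects who are still on treatment will be randomized (1:1) to one of the two cohorts"), and the dosing row of Table 5.1-2 ("At 1 year (52 weeks) all subjects that remain on treatment will be randomized to Arm A or Arm B").
- **Still benefiting.** The synopsis sample-size text ("who are still benefiting from therapy after 52 weeks (estimated to be between 99 and 322 subjects) will be randomized"), Section 8.1.1 in similar terms, Section 4.1 ("the subjects who are still on the study and benefiting from the therapy will be randomized (1:1) via IVRS"), Section 4.2 ("are still benefiting from the nivolumab treatment will be randomized (1:1) via IVRS to one of the two cohorts") and the randomization row of Table 5.1-2 ("Subjects that are still on study and benefiting from treatment will be randomized 1:1 to Cohort A or B").

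Treatment past a first progression is allowed. Section 4.3.4 opens: "Subjects treated with nivolumab will be permitted to continue treatment beyond initial RECIST 1.1 defined progressive disease (PD". Its first condition is clinical benefit as judged by the investigator, and it ends treatment for good once further progression is documented. Section 3.4.3 adds a second route: limited-field palliative radiotherapy counts as progression of the non-target lesion, and further dosing then follows 4.3.4.

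Section 8.3.3 defines PFS from first dose to first documented progression or death, and ends DOR at the initial documented progression or death. Section 8.4.4.2 summarises both by Kaplan-Meier for all randomised subjects in Cohorts A and B, a set that Section 8.2 defines with no condition on progression. No landmark, new time origin or exclusion for earlier progression appears in the readable text.

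**The concern.** A subject who progressed at, say, week 33, stayed on drug under 4.3.4 and reached week 52 fits both wordings of who is randomised. That subject's PFS event, and DOR event if a confirmed responder, was fixed before allocation and cannot depend on whether treatment then stops or continues. Such events enter both cohort curves and dilute the contrast.

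This is the study's only randomised comparison, and Section 1.1.2.1 gives its purpose as learning how treatment duration affects maintenance of tumour response. PFS and DOR are the measures closest to that purpose. The comparison is nevertheless exploratory: Kaplan-Meier summaries with confidence intervals are planned, and no hazard ratio, test or difference. OS does not depend on progression, and the primary and secondary safety objectives are not touched.

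**Working it through.** **1. The plan's own figure.** Inputs: 10 of 37 (synopsis, 8.1.1) and 780 treated (8.1). The Wald interval is 0.270 ± 1.96 × √(0.270 × 0.730 / 37) = 12.7% to 41.3%. Then 780 × 0.127 = 99.1 and 780 × 0.413 = 322.1, which reproduces 99 to 322. Section 3.1 now plans 1280 treated: 1280 × 0.127 = 162.6 and 1280 × 0.413 = 528.6, or about 163 to 529.

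**2. The label on 10 of 37.** The synopsis and Sections 1.1.1 and 1.1.2.1 describe these subjects as still on treatment. Section 8.1.1 describes the same 10 as progression-free. The planning text therefore does not keep apart the two states that matter here.

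**3. What is known of f**, the share of randomised subjects with progression already documented. The protocol gives no value. Section 1.1.2.1 says 9 of the 10 Phase 1 subjects still treated at one year had durable responses; the tenth is not described, and 8.1.1 calls all 10 progression-free. That suggests 0 or at most 1 of 10, with exact 95% intervals of 0 to 30.8% or 0.3 to 44.5%: too few to fix f. The values 5% and 10% below are assumptions, and 20% is an upper illustration.

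**4. Effect on the curves.** With share f in each cohort progressing before week 52, the expected cohort curve at time u after week 52 is (1 − f) × S(u), where S is PFS among those progression-free at randomisation. The vertical gap is multiplied by 1 − f. With S(u) = exp(−λu), the median lies at u = ln(2(1 − f))/λ, so the gap in medians is multiplied by ln(2(1 − f))/ln 2. The example assumes medians of 9 and 15 months after week 52, a true gap of 6.0 months.

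| f | vertical gap × | gap in medians × | 6.0-month gap seen as |
|---|---|---|---|
| 5% | 0.95 | ln 1.9 / ln 2 = 0.926 | 5.6 months |
| 10% | 0.90 | ln 1.8 / ln 2 = 0.848 | 5.1 months |
| 20% | 0.80 | ln 1.6 / ln 2 = 0.678 | 4.1 months |

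**5. Against sampling error.** In 4,000 simulated trials per setting (same medians, early progressions spread uniformly over 2 to 11.9 months), the standard deviation of the gap in medians at f = 0 was 2.79 months with 163 randomised and 1.56 with 529. The shift in standard-deviation units was:

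| f | 163 randomised | 529 randomised |
|---|---|---|
| 5% | 0.16 | 0.24 |
| 10% | 0.32 | 0.55 |
| 20% | 0.68 | 1.19 |

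The analytic values for 529 are 0.28, 0.59 and 1.24.

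**6. Chance imbalance in f.** The standard deviation of the between-cohort difference in f is √(4f(1 − f)/n). At f = 10% this is √(0.36/163) = 4.7 points or √(0.36/529) = 2.6 points.

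**7. Scan timing.** Scans at weeks 9 + 8k fall at 41, 49 and 57, so weeks 49 and 57 lie either side of allocation. Appendix 1 (3.3 and 4.4) dates a later-confirmed progression back to the scan where it was first suspected.

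DOR is not quantified. It is affected only through confirmed responders who progressed before week 52 and stayed on drug.

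**The case against.** The strongest reply is that unprogressed subjects were meant. Section 3.5 keeps Cohort B off drug until progression makes them eligible for retreatment, which presumes it has not yet happened. Section 3.1 continues Cohort A until progression, Section 3.2 speaks of Cohort B subjects who did not progress in follow-up, and Section 8.1.1 applies a progression-free rate. Cohort B text and two analysis populations in 8.2 are redacted and the schematic is not shown, so a rule could stand there. No passage ties the undefined word benefiting to the benefit condition in 4.3.4. This limits certainty, but the readable analysis text contains no such restriction; if one was intended, Section 8 should state it.

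Second, the effect may be small. The 4.3.4 stop at further progression limits f, and at f up to 10% the shift is below sampling error. That stands, and it keeps the point modest.

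Third, the pull together holds only in expectation. In one trial, chance imbalance in f could also push the curves apart, and the shape of each curve after week 52 among those still at risk is unbiased. Both are true. Neither makes pre-allocation events informative about treatment duration.

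Fourth, since randomisation falls at 52 ± 2 weeks (Section 4.2), moving the time origin mostly subtracts a constant. Correct: it is the exclusion that removes the dilution.

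**Conclusion.** The concern holds on the visible text. Followed as written, the plan can put PFS and DOR events that predate allocation into the cohort summaries, shrinking the expected vertical PFS gap by the share f and the gap in medians by somewhat more (factors 0.93, 0.85 and 0.68 at f = 5%, 10% and 20%). These sizes rest on assumed f, equal expected f in both cohorts, and exponential PFS after week 52; the months also rest on the assumed medians of 9 and 15. Confidence is medium, because f is unknown and redacted text could contain a restriction. It is worth correcting because the correction is cheap, not because a main conclusion is at risk.

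Two inconsistencies stand whatever f is, though they do not bear on the size of the PFS effect: the two labels on 10 of 37, and the 99 to 322 estimate that still rests on 780 treated.

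**What to change.** 1. In 8.4.4.2, summarise Cohort A/B PFS from the date of randomisation, in randomised subjects with no RECIST 1.1 progression documented at that time. Restrict cohort DOR to confirmed responders meeting the same condition.
2. Do not exclude subjects whose progression is confirmed after randomisation and dated back to before it. The confirming read is open-label, so that exclusion could depend on cohort. Count such progression as an event, either at randomisation or at the confirming scan, by one rule stated in advance for both cohorts. Either choice departs from the Appendix 1 dating for this analysis, and the text should say so.
3. Report by cohort the number randomised after documented progression. Keep OS and safety in all randomised subjects.
4. Reconcile the wordings of who is randomised (synopsis, 3.1, 4.1, 4.2, 8.1.1, both rows of Table 5.1-2), label 10 of 37 consistently (synopsis, 1.1.1, 1.1.2.1, 8.1.1), and restate 99 to 322 for 1280 treated: about 163 to 529 at the same rates.

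The cost is wording. No new assessments are needed, but progression status as recorded at randomisation must be kept, because the derived date can later move back. A criterion fixed at randomisation preserves the randomised comparison. The price is a smaller set for cohort PFS: of 163 to 529 randomised, about 8 to 26 fewer at f = 5%, 16 to 53 at 10% and 33 to 106 at 20%. Cohort DOR loses the corresponding responders.
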